7.2 Efficacy Assessments

Tumor assessments will include imaging (e.g., CT, MRI, x-ray, fluorodeoxyglucose positron emission tomography [FDG-PET]) and caliper measurements, as applicable, and will be performed at the time points specified in [Table 10](#) and [Table 11](#).

Efficacy assessments include determination of objective response using RECIST v1.1. For patients who have initial evidence of radiological PD by RECIST v1.1, it will be at the discretion of the Investigator to keep a patient on study treatment or to stop study treatment until repeat imaging is performed approximately 4 weeks later in order to confirm PD per irRC. Patients with confirmed irPD should discontinue treatment. Patients with a declining ECOG PS, deteriorating clinical symptoms or rapid progression of disease/progression at critical anatomical sites (i.e., CNS) should be considered for treatment discontinuation based on clinical judgment.

All data acquired for efficacy purposes (e.g., CT, MRI, x-ray, FDG-PET, pathology reports, caliper measurements and measurements of tumor markers) obtained at Screening and while on study, including any off-schedule imaging studies performed, should be made available if requested by the Sponsor for central assessment by an independent reviewer.

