7.2.2 Immune-Related Response Criteria

Response to treatment will also be measured using irRC ([Wolchok et al 2009](#)), as assessed by the Investigators. Confirmation of an immune-related complete response (irCR), immune-related partial response (irPR) and immune-related disease progression will be required by a repeat, consecutive assessment no less than 4 weeks from the date first documented. The details of the irRC assessment can be found in [APPENDIX 6](#).

CC

[REDACTED]

[REDACTED]

[REDACTED]

[REDACTED]

CCI [REDACTED]

[REDACTED]

[REDACTED]

[REDACTED]

CCI [REDACTED]

[REDACTED]

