Patients are considered to have irPR or irSD even if new lesions are present, as long as they met the respective thresholds of response described above. Furthermore, patients are not considered to have irPD if new lesions are present and the tumor burden of all lesions did not increase by $\geq 25\%$. In contrast to irCR, irPR, and irPD, a response of irSD does not require confirmation. It is important to note that irCR, irPR, and irSD include all patients with CR, PR or SD by RECIST as well as those patients who shift to these irRC categories from RECIST PD. Patients with irSD, particularly those with slow-declining tumor burden $\geq 25\%$ from baseline at the last tumor assessment, are considered clinically meaningful because they show an objectively measurable reduction in tumor burden without reaching the 50% threshold that defines irPR (ie, this represents an objectively measured reduction not commonly observed in the natural history of advanced melanoma patients).

If a patient is classified as having irPD at a postbaseline tumor assessment, then confirmation of irPD by a second scan in the absence of a rapid clinical deterioration is required. The definition of confirmation of progression represents an increase in tumor burden $\geq 25\%$ compared with nadir at 2 consecutive time points at least 4 weeks apart. It is recommended that this be done at the discretion of the Investigator because follow-up with observation alone may not be appropriate for patients with a rapid decline in performance status. Confirmation of irPD allows for the capture of all observed responses using the irRC (Table B), as most of these late-responding patients have a trend toward response within 4 weeks after initial irPD. Whereas

RECIST consider any new measurable lesion to indicate PD, determination of immune-related best overall response (irBOR) is based on changes in total tumor burden from baseline (nadir, for irPD) tumor assessment, regardless of any initial increase in baseline lesions or the appearance of new lesions.

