#### 7.5.1 Objective Response Rate

ORR is defined as the proportion of patients who have achieved a best overall response (BOR) of complete response (CR) or partial response (PR) as determined by Investigator review of radiographic disease assessments per RECIST v1.1. Both confirmed and unconfirmed ORR will be summarized, but the primary analysis will be based on confirmed responses.

The BOR is defined as the best response recorded from the study start date until progression and will be determined programmatically based on the Investigator’s assessment of tumor response at each time point per RECIST v1.1. Only tumor assessments performed before the start of any subsequent anticancer therapies and not later than 30 days after last dose of study drug will be considered in the assessment of best overall response. Clinical deterioration or clinical progression noted on the End of Treatment Disposition eCRF will not be considered as documented disease progression for the purposes of the ORR calculation.

The confirmed BOR for each patient is determined from the sequence of overall timepoint (lesion) responses according to the following rules below:

CR = at least two determinations of CR at least 4 weeks apart before progression, where confirmation required, or one determination of CR prior to progression, where confirmation not required.

PR = at least two determinations of PR or better at least 4 weeks apart before progression (and not qualifying for a CR), where confirmation required, or one determination of PR prior to progression, where confirmation not required.

SD = an assessment of SD or better > 6 weeks after start of treatment (and not qualifying for PD, PR or CR).

PD = progression  $\leq$  9 weeks after start of treatment (and not qualifying for CR, PR, or SD).

NE (Not Evaluable) = all other cases (i.e. not qualifying for confirmed CR or PR and without SD after more than 6 weeks or early progression within the first 9 weeks).

Patients with confirmed best overall response 'Not Evaluable' will be summarized by reason for having unknown status. The following reasons will be used:

- No baseline assessment
- No adequate post-baseline assessment
- All post-baseline assessments have overall response of "NE"
- New anticancer therapy started before first post-baseline assessment
- SD occurred  $\leq$  6 weeks after the start of treatment

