#### **7.5.5 Immune-related Response Rate**

Immune-related RR (irRR) is defined as the proportion of patients who achieve immune-related best overall response (irBOR) of immune-related CR (irCR) or immune-related PR (irPR), as determined by the Investigator per irRC, where irBOR is the best response using irRC recorded from the start of study treatment until the end of treatment.

The confirmed irBOR for each patient is determined from the sequence of overall timepoint (lesion) responses per irRC as summarized in Appendix 6 in the study protocol. The derivation of BOR with confirmation requirement as defined in Section 7.5.1 will be used to determine the

irBOR. In addition, Immune-related PD (irPD) needs to be confirmed by a repeat, consecutive assessment no less than 4 weeks from the first documented date.

The irRR will be calculated along with the two-sided exact Clopper-Pearson 95% CIs. In addition, the number and percentage of patients in each BOR category, i.e., irCR, irPR, immune-related SD (irSD), irPD, and immune-related Unevaluable (irUnevaluable) will be summarized.

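### The irPD-confirming scan is timed at about 4 weeks with no minimum, and SAP 7.5.5 can exclude a valid one after treatment stops: a small effect with a cheap fix

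*Protocol*

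**What the plan says.** **Scan instruction.** Protocol 7.2 leaves it to the investigator to continue or stop treatment after first RECIST progression "until repeat imaging is performed approximately 4 weeks later in order to confirm PD per irRC". The Synopsis, Protocol 4.1 and SAP 3.1 use the same wording. No minimum or window is attached, and neither schedule of events (Tables 10 and 11) has a row for this scan.

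**Confirmation rule.** Protocol 7.2.2 requires irPD to be confirmed by a "repeat, consecutive assessment no less than 4 weeks from the date first documented". Appendix 6 asks for a tumor burden increase of at least 25% "compared with nadir at 2 consecutive time points at least 4 weeks apart", and exempts rapid clinical deterioration from the second scan. SAP 7.5.5 says irPD must be "confirmed by a repeat, consecutive assessment no less than 4 weeks from the first documented date". None of the three gives a tolerance.

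**Which scans count.** SAP 7.5.5 records irBOR "from the start of study treatment until the end of treatment". It then says: "The derivation of BOR with confirmation requirement as defined in Section 7.5.1 will be used to determine the" irBOR. Section 7.5.1 limits the usable scans to those before subsequent anticancer therapy and "not later than 30 days after last dose of study drug will be considered in the assessment of best overall response". SAP 7.1.1 defines study drug as either agent.

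**The concern.** The instruction that sites act on and the rule that the analysis applies differ at the early edge. A site that schedules the repeat scan a day or two short of 4 weeks has done what it was told, yet that scan cannot confirm irPD even if the tumor burden is still at least 25% above nadir.

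The late edge raises a separate problem. Protocol 7.2 expressly allows treatment to stop at first progression. The analysis may then have only a few days in which a scan is both late enough to confirm and early enough to count. A patient who has truly progressed could be reported as irUnevaluable. The irBOR categories are tabulated, and irPFS is a secondary endpoint in every cohort.

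**Working it through.** No published figure has to be reproduced. The check compares texts and counts days.

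**Inputs**
- 1 week = 7 days (SAP 7.1.7), so 4 weeks = 28 days.
- Minimum gap for irPD: 28 days (Protocol 7.2.2, Appendix 6, SAP 7.5.5).
- Latest scan counted for BOR: last dose + 30 days (SAP 7.5.1).
- Cycles of 21 days; scans at Cycle 3 Day 1 ± 7 days, then about every 6 weeks (Protocol Table 11).
- PD as a best response: progression no later than 9 weeks after start (SAP 7.5.1), i.e. 9 × 7 = 63 days.

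Let Day 0 be the first documented irPD, taken to be the same scan as first RECIST progression. Let k be the day of the last dose of either drug relative to Day 0.

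**Step 1: early edge.** Days 25, 26 and 27 are 25/7 = 3.57, 26/7 = 3.71 and 27/7 = 3.86 weeks. Each can fairly be called about 4 weeks, and each is short of 28 days. These days are illustrative, because the documents set no window. A later scan, counted from Day 0, can still confirm if the patient goes on being scanned. That may not happen: after the 30-day safety visit, Protocol 8.5 calls for scans only if clinically indicated, and encourages continued scanning only for patients who stopped for a reason other than progression.

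**Step 2: late edge, if the 30-day limit applies to irBOR.** A scan must fall on or after Day 28 and on or before Day 30 + k. Usable days = max(0, (30 + k) − 28 + 1) = max(0, k + 3).

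| Last dose, k | Usable scan days | Number |
|---|---|---|
| −3 or earlier | none | 0 |
| −2 | 28 | 1 |
| −1 | 28–29 | 2 |
| 0 | 28–30 | 3 |
| 5 | 28–35 | 8 |
| 7 | 28–37 | 10 |

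A Day 28–35 window lies wholly inside the limit only if 30 + k ≥ 35, i.e. k ≥ 5. The limit runs from last dose, so it binds during a hold as well: if irPD is confirmed, treatment does not resume and the last dose stays where it was. If dosing continues to the repeat scan, only the 28-day minimum matters.

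**Step 3: end-of-treatment wording.** SAP 7.1.9.6 takes the end-of-treatment date from the disposition page, as the date of discontinuation. A patient on hold would normally reach that date after the scan. A patient stopped for good at first irPD reaches it before the scan, and a literal reading of 7.5.5 then leaves the scan out.

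**Step 4: who can be affected.** Cycle 3 Day 1 is 42 days after start, so the first scheduled scan falls at 35–49 days. Cycle 5 Day 1 is 84 days after start, so the second falls at 77–91 days. Of these, only the first is within 63 days. A patient with unconfirmed irPD at that scan falls into the residual category of 7.5.1, which covers those without a confirmed response and "without SD after more than 6 weeks or early progression within the first 9 weeks".

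**Step 5: other endpoints.** Moving between irPD and irUnevaluable leaves a patient a non-responder in the same denominator, so irRR does not change. Primary ORR and the Simon rules use RECIST, which does not depend on irPD. SAP 7.5.6 takes its censoring from 7.5.3, which has no limit tied to last dose, so the late edge does not reach irPFS. The early edge might: if progression there means confirmed irPD, a patient whose only repeat scan was early has no confirmed event.

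**The case against.** The strongest reply is that the minimum is already in place. The instruction orders the scan to confirm PD per irRC, and 7.2.2, shortly afterwards in the same section, gives the irRC minimum and points to Appendix 6. A site that reads both will scan at 4 weeks or shortly after. This stands: a reader might infer that the protocol contradicts itself, but a scan on Day 28 or slightly later satisfies every text. Early scans are also often recoverable, since routine imaging continues about every 6 weeks while a patient is followed. A reader who concludes that one early scan rules out confirmation goes too far, although the word consecutive leaves it unclear how an early intermediate scan is treated.

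The second reply is that the 30-day limit may not apply to irBOR at all. SAP 7.5.5 gives irBOR its own window, and the cross-reference to 7.5.1 can be read as importing only the confirmation and category rules. That reading is open, so the day counts in Step 2 are conditional. It does not clear the plan, however: on that reading the end-of-treatment wording governs, and it is stricter for patients stopped for good.

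It is also fair that Protocol 7.2 describes a stop pending the scan, that the zero-day case requires both drugs to have been withheld before irPD was seen, and that nothing in the documents shows how often either occurs.

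**Conclusion.** The point holds as a minor one. The scan instruction lacks the 28-day minimum that the analysis requires, and SAP 7.5.5 does not secure a valid confirmatory scan for a patient whose treatment stopped or was held at first irPD.

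The reach is narrow: irPD versus irUnevaluable for patients progressing at the first scheduled scan, and for early scans possibly an irPFS event versus censoring. No frequency can be given, because the documents contain no repeat-scan dates.

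A reader might infer that response rates or the stage 1 decisions are at risk, or that patients must stay on treatment until a qualifying scan. The documents support neither. The primary endpoint and the Simon rules rest on RECIST, irRR does not move, and Protocol 7.2 allows discontinuation on clinical judgment.

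Assumptions: first RECIST progression and first irPD fall on the same scan; the 3-day result requires the 30-day limit to apply to irBOR and the last dose to fall on Day 0; and unconfirmed irPD is classified by the 7.5.1 categories. The protocol reviewed is Version 4, while the SAP cites Version 5. SAP 3.1 still carries the loose timing.

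**What to change.** In the Synopsis, Protocol 4.1, Protocol 7.2 and SAP 3.1, change the timing to *at least 4 weeks (28 days) later, e.g. 28 to 35 days*.

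In SAP 7.5.5, add a sentence: a scan in that window, done before any new anticancer therapy, counts for confirming irPD regardless of the 30-day and end-of-treatment limits. Restrict the exception to confirming irPD, so that it cannot add responders. It is needed because a 28-to-35-day window fits inside the 30-day limit only when the last dose is at least 5 days after first irPD.

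The cost is one phrase in four places and one SAP sentence. No extra scans are needed and no sample size or error rate changes. The downside is that for some patients the repeat scan, and the decision that follows it, comes a few days later.

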7.2.1 Response Criteria in Solid Tumors

Response to treatment will be measured using RECIST v1.1 ([APPENDIX 5](#)), as assessed by the Investigators. Confirmation of CR and PR will be required by a repeat, consecutive assessment no less than 4 weeks from the date first documented.

7.2.2 Immune-Related Response Criteria

Response to treatment will also be measured using irRC ([Wolchok et al 2009](#)), as assessed by the Investigators. Confirmation of an immune-related complete response (irCR), immune-related partial response (irPR) and immune-related disease progression will be required by a repeat, consecutive assessment no less than 4 weeks from the date first documented. The details of the irRC assessment can be found in [APPENDIX 6](#).

CC

[REDACTED]

[REDACTED]

[REDACTED]

[REDACTED]

CCI [REDACTED]

[REDACTED]

[REDACTED]

[REDACTED]

CCI [REDACTED]

[REDACTED]

7.3.1.3 Tumor Markers (Phase 2 Only)

Tumor markers, such as cancer antigen 19-9 (CA 19-9) and cancer antigen 125 (CA-125), will be measured as appropriate for tumor type from serum samples obtained from patients in Phase 2.

7.4 Pharmacokinetic Assessments

Venous blood samples for measurement of plasma concentrations of ARRY-382 and its metabolites (AR00469099 [an N-oxide metabolite], AR00469100 [an N-desmethyl metabolite], and AR00470870 [a sulfate metabolite]) will be drawn at the time points specified in [Table 10](#) and [Table 11](#). Pembrolizumab concentrations are not planned to be measured because no drug-drug interaction is expected. However, remaining PK plasma samples may be used to assess pembrolizumab concentrations, CCI [REDACTED] or concomitant medications on an ad hoc basis. Complete instructions for sample collection, processing, handling and shipment will be provided in the Laboratory Manual.

Predose PK samples must be collected within 120 minutes prior to administration of ARRY-382. Postdose PK samples will be collected at 1 hr (± 5 min), 2 hr (± 10 min), 4 hr (± 20 min), and 8 hr (± 30 min) after administration of ARRY-382 on Cycle 1 Day 1 and Cycle 2 Day 1. Trough PK blood samples will be collected predose on Cycle 1 Day 15 and Day 1 of Cycles 3 through 6.

If a patient experiences an AE that results in an unscheduled visit or meets SAE criteria, a blood sample for measurement of plasma concentrations of ARRY-382 and its metabolites (AR00469099, AR00469100, and AR00470870) should be collected if less than 24 hours has elapsed since the last dose of study drug, if possible.

If vomiting occurs within 4 hours following study drug administration on the day of PK blood sampling, the time (using the 24-hour clock) of vomiting should be recorded on the transmittal forms that accompany the sample and that dose of study drug should not be re-administered.

7.5 Safety Assessments

7.5.1 Adverse Events

Adverse events will be assessed by direct observation and patient interviews. Patients should be questioned using non-leading questions. Assessment and reporting of AEs is described in detail in [Section 10.0](#) and will be completed at the time points specified in [Table 10](#) and [Table 11](#).

7.5.2 Clinical Laboratory Tests

Clinical laboratory tests include hematology, coagulation, clinical chemistry, thyroid panel, and urinalysis ([Table 9](#)) and will be collected at the time points specified in [Table 10](#) and [Table 11](#). It is expected that local laboratories will be used for all protocol-specified and unscheduled laboratory tests related to safety. Depending on the availability of certain tests at local laboratories, some protocol-specified laboratory tests may be performed outside of local laboratories.

Table 9: Clinical Laboratory Tests

Hematology	Chemistry	Urinalysis	Others
Hemoglobin	BUN	Appearance	
 • HBsAg and HCV serology (RNA, qualitative if serology positive) (screening only) • Serum or urine pregnancy test^b (females of childbearing potential only)
Hematocrit	Urea	Color	
RBC	Uric acid	Specific gravity	
Platelets	Creatinine	pH	
WBC	Creatinine clearance ^a	Myoglobin ^c	
Neutrophils	Total protein	Protein	
Lymphocytes	Albumin	Glucose	
Monocytes	Alkaline phosphatase	Ketones	
Eosinophils	AST	Blood	
Basophils	ALT	Nitrite	
	Lactate dehydrogenase	Leukocyte esterase	
	Total bilirubin	If urinalysis is abnormal, then microscopy:	
	Indirect bilirubin	
 • WBC • RBC • Bacteria • Epithelial cells • Casts 	
	Direct bilirubin (if total bilirubin values are above normal)		
Coagulation			
INR	Amylase		
PT	Lipase		
aPTT/PTT	Aldolase		
	CK		
Thyroid Panel	CK isoenzymes ^c		
TSH	Glucose		
T3, free	Sodium		
T4, free	Potassium		
	Chloride		
	Bicarbonate		
	Calcium		
	Magnesium		
	Phosphorus		

ALT = alanine aminotransferase; aPTT = activated partial thromboplastin time; AST = aspartate aminotransferase; BUN = blood urea nitrogen; CK = creatine kinase; HBsAg = hepatitis B surface antigen; HCV = hepatitis C virus; INR = International Normalized Ratio; PT = prothrombin time; PTT=partial thromboplastin time; RBC = red blood cells; RNA = ribonucleic acid; T3 = triiodothyronine; T4 = thyroxine; TSH = thyroid-stimulating hormone; WBC = white blood cells

^a Creatinine clearance will be calculated using the Cockcroft-Gault formula $[(140 - \text{age}) * \text{body mass (kg)} / \text{creatinine (mg/dL)} * 72] * 0.85$ for females or 1.00 for males.

^b Serum pregnancy test required at screening only; serum or urine pregnancy tests will be allowed at subsequent time points.

^c Measurement of CK isoenzymes and urine myoglobin only necessary if total CK is \geq Grade 2, unless there are cardiac signs and symptoms. If cardiac signs and symptoms are present, measure CK isoenzymes and urine myoglobin if total CK is any grade above normal.

Site-specific handling instructions for hematology, coagulation, clinical chemistry, thyroid panel, and urinalysis samples should be followed. Screening results will be assessed by the Investigator to determine patient eligibility. Day 1 results (or assessments allowed within 96 hours prior to Day 1) will be assessed by the Investigator prior to first dose of study treatment; clinical chemistry and coagulation test results must be reviewed before the first dose of study drug is administered in each cycle. Additional clinical laboratory tests may be obtained at any time during the study at the Investigator's discretion. Clinically significant findings should be followed to resolution or stabilization.

Blood and urine sample collections on dosing days must be performed prior to study treatment administration. Laboratory test results required to make decisions regarding potential dose modifications (as specified in [Section 6.3](#)) should be reviewed prior to study treatment administration.

7.5.3 Physical Examination

Physical examinations, including weight, will be performed by trained medical personnel at the time points specified in [Table 10](#) and [Table 11](#). Height will be measured only at screening. All physical examinations occurring on dosing days must be performed prior to study drug administration.

7.5.4 Vital Signs

Vital signs (blood pressure, pulse, and temperature) will be measured per institutional standards at the time points specified in [Table 10](#) and [Table 11](#). Any treatment-emergent abnormal findings will be recorded as AEs.

7.5.5 Electrocardiogram

Triplicate 12-lead ECGs will be performed at the time points specified in [Table 10](#) and [Table 11](#). At each measurement, 3 serial ECGs will be obtained over a period of approximately 5 to 10 minutes. The mean of the triplicate ECG measurements performed at predose on Day 1 will serve as each patient's baseline value for all postdose comparisons.

In some cases, it may be appropriate to repeat an abnormal ECG. However, if the Investigator is able to interpret the ECG, then an abnormal ECG does not need to be repeated. When ECGs are to be performed at the same time point as a blood collection, ECGs should be performed first.

QT interval values will be corrected using Fridericia's formula (QTcF).

All ECGs will be submitted for central assessment.

